## Proposal for “Randomized Comparison of Mindfulness versus Group Support for Treatment of Low Sexual Desire in Women”

### JUSTIFICATION:

Population-based studies suggest that difficulties with low sexual desire and insufficient sexual arousal are extremely common in women across the life cycle. Our understanding of the precise mechanisms that control female sexual response is at present incomplete. Sexual response, which includes sexual motivation, interest, and arousal, has been conceptualized as a complex interaction between physiological and psychological components (Everaerd, Laan, Both, van der Velde, 2000; Rosen & Beck, 1988), and mounting evidence suggests that sexual desire and arousal may be two aspects of the same sexual response process. Several studies have found a high degree of comorbidity between Hypoactive sexual desire disorder (HSDD) and Female sexual arousal disorder (FSAD; Brotto 2011; Fugl-Meyer& Fugl-Meyer, 2002). Moreover, scores on desire and arousal domains, using different instruments, are typically highly correlated with one another (Brauer, Lakeman, van Lunsen, and Laan 2010; Laan, Termeer, van Lunsen, Zimmerman, Coelingh Bennink, 2010; Nobre, Pinto-Gouveia, Gomes, 2006; Rosen et al., 2000; ter Kuile, Brauer, and Laan, 2006). This high correlation was found both in women with and without FSAD (Wiegel, Meston, and Rosen, 2005). In their longitudinal research on mid-life women, which contributed to the development of a model of women’s sexuality, Dennerstein and colleagues found that items tapping into women’s sexual arousal and responsiveness could not be separated from items tapping into sexual desire (Dennerstein, Lehert, and Burger, 2005). A central tenet of the Incentive Motivation Model for sexual response is that sexual desire and sexual arousal emerge, together, in response to effective sexual cues. Sexual desire and sexual arousal may even represent different sides of the same sexual coin. If desire and arousal are to be distinguished, it is likely only at a phenomenological level, with desire defined as the willingness to behave sexually and sexual arousal reflecting the subjective experience of genital changes (Laan and Both, 2008).

In one of the most recent examinations of population prevalence of low desire, the “Prevalence of Female Sexual Problems Associated with Distress and Determinants of Treatment Seeking” (PRESIDE) study examined 31,581 American women aged 18-102 (mean age 49; Shifren et al. 2008). The Female Sexual Distress Scale (FSDS; Derogatis et al., 2002) was used to measure sex-related distress and the item “How often do you desire to engage in sexual activity” was used to capture low desire. Low desire, defined as a response of “never” or “rarely” to this item, was found in 38.7% of the sample and distress, defined as a score  $> 15$  on the FSDS, was found in 22.8%. The overall estimate of HSDD, taking into account both criteria, was found to be 10.0%. Even considering the drop in prevalence when low desire and distress together are assessed, this continues to be the most frequent complaint seen in sex therapy clinics, and the majority of women with any sexual difficulty (i.e., desire, arousal, orgasm, or pain-related) state that their low sexual desire is the cause of their sexual difficulties (Hayes, et al., 2006).

Population-based estimates suggest that lubrication difficulty, as a specific symptom of Female Sexual Arousal Disorder (FSAD), affects from 11-19% of women younger than 30, up to 24-27% of women older than 50 (Fugl-Meyer & Fugl-Meyer, 1999; Laumann, Paik, & Rosen, 1999), and may be as high as 75% for those women seeking routine gynecological care (Nusbaum et al., 2000). Lack of subjective (sometimes called cognitive or mental) sexual arousal during the sexual experience, especially when intercourse frequency is more tuned to the higher needs of the partner, is a more common complaint among women presenting clinically. Despite the fact that complaints of sexual arousal difficulty and associated distress are extremely common in the clinical setting, evidence based treatments to address FSAD are non-existent.

Despite their high prevalence, sexual interest, desire, and arousal concerns remain without effective treatment today. Moreover, there are no Food and Drug Administration (FDA) or Health Canada approved pharmaceutical products available to treat these highly distressing symptoms.

Our laboratory has published evidence showing the efficacy of a mindfulness-based cognitive behavioural therapy for the treatment of distressing loss of desire/arousal in women (Brotto, Basson, Luria, 2008; Brotto, Heiman, et al., 2008; Brotto, Erskine, Carey, et al., 2012; Brotto, Seal, & Rellini, 2012). Our protocol included four sessions delivered in group format with two facilitators and was based on empirically supported techniques in other areas of female sexual dysfunction (e.g., sensate focus, challenging maladaptive cognitions and sexual myths). The ingredients were adapted from a variety of sources including (1) *Becoming Orgasmic* by Heiman and LoPiccolo (1988), which is an empirically-supported behavioural treatment for women with lifelong orgasmic disorder, (2) *Seven principles for making marriage work* by Gottman (1999); (3) *The Miracle of Mindfulness* by Thich Nhat Hahn (1976); (4) *Full Catastrophe Living* by Jon Kabat-Zinn (1990) and (4) *Progressive Relaxation* by Edmund Jacobson (1938). It involved in-session didactic material as well as in-session mindfulness practices followed by daily homework activities between sessions.

In our clinical experience, mindfulness techniques, with the aim of guiding attention into the present, can be a very effective component of care among women with sexual difficulties and we have been using mindfulness techniques for women with loss of desire and arousal. The proposed study, “Randomized Comparison of Mindfulness versus Group Support for Treatment of Low Sexual Desire in Women” compares the effectiveness of group mindfulness-based cognitive therapy (MBCT) and support. The MBCT group expands on our previous 4-session intervention by incorporating a larger proportion of mindfulness practice and information in session, and expanding the sessions to eight weekly sessions to make it more in line with other mindfulness based interventions for depression that have received widespread empirical attention and support.

#### PURPOSE:

This study utilizes a mindfulness-based psychoeducational treatment approach that is based on our 4-session effective treatment protocol. As with the 4-session treatment, the currently proposed 8-session MBCT group is based on a variety of empirically supported techniques, and integrates elements of education, mindfulness skills, and sex therapy. The purpose of this study is to determine whether an 8-session intervention is effective in reducing women’s sexual distress, improving their sexual response, and increasing their mindful skills. To date, many women who have received our 4-session intervention have indicated that having more than 4 sessions would be beneficial. As well, other integrated mindfulness/cognitive behavioral treatments (e.g., Mindfulness-Based Cognitive Therapy for depression; Segal, Williams, & Teasdale, 2002) are 8-sessions in length and provide increased opportunity for participants to practice the skills they are learning in session.

#### HYPOTHESES:

1. Compared to baseline, the MBCT group will have significant post-treatment improvements in self-report measures of: (a) sexual distress; (b) sexual desire, subjective sexual arousal, perception of genital arousal, and sexual pleasure; (c) relationship satisfaction; (d) depressive symptoms and rumination; (e) perceived stress, general anxiety, anxiety sensitivity, and sexuality-related situational anxiety (as self-reported at the sexual arousal assessment); and (f) mindfulness, self-compassion, non-attachment, and interoceptive awareness.
2. Compared to baseline, the MBCT group will have significant post-treatment improvements in laboratory physiological measures of: (a) genital sexual response as measured by a vaginal photoplethysmograph, (b) interoceptive awareness, as measured

by a heart rate perception task, (c) cortisol:DHEA ratio as measured by hormonal assays of saliva samples, and (d) a significant decrease in C-reactive protein as measured by hormonal assays of saliva samples.

3. We hypothesize that the changes in the endpoints listed in #1 or #2 will be significantly greater in the MBCT group than in the support group.
4. We hypothesize that participation in the MBCT group will significantly increase concordance.
5. Mindfulness, self-compassion, and interoceptive awareness will significantly mediate improvements in sexual distress and desire in the MBCT group at all post-treatment assessment points.
6. Expectations of change with treatment will not significantly moderate improvements in sexual distress and desire in the MBCT group.
7. Participants' impressions of change will be significantly greater in the MBCT group compared to the support group at all post-treatment assessment points.
8. We hypothesize that participants with sexual desire issues will see an improvement (fewer breaks in the cycle) throughout the course of the eight-week treatment.

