#### OBJECTIVES:

The main objective for this study is to test the MBCT group with women who are currently seeking treatment for low sexual interest/desire and/or arousal and compare it to a support group.

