
consent form. Following enrolment, she will be randomized to either group mindfulness-based therapy or support group therapy and will be registered for the next study group. Arrangements will also be made to complete the saliva sampling, pre-treatment questionnaires, and the sexual psychophysiological assessment.

Inclusion criteria for treatment group includes: any woman between the ages of 19-65, fluent in English, and who experiences distressing sexual interest/desire and or sexual arousal concerns. Exclusion criteria include: a psychiatric or medical condition precluding group attendance or homework completion, and Borderline Personality Disorder (for which mindfulness meditation may cause dissociation and is therefore counter-indicated; Sachse, Keville, & Feigenbaum, 2011).

Procedures: Participants will be randomly assigned to either the MBCT group or the support group (control condition). The purpose of the support group is to control for any effect of the sexuality education, discussion, and support provided in the MBCT group.

All participants will meet in-person with a trained graduate student in clinical or counselling psychology to ask any further questions about the study, to review study protocol, and discuss participant remuneration- \$55/assessment (\$25 per questionnaire package plus \$30/ per laboratory-based assessment and at-home saliva sample collection) for each of the four times completed. Participants will receive their saliva sampling kit (which includes all necessary sampling equipment) and detailed written and verbal instructions on how to collect their samples.

After saliva samples have been collected, participants will return their saliva sampling kits to the Study Coordinator when they take part in an individual sexual psychophysiological assessment in the PI's laboratory (UBC Sexual Health Lab) located in the Diamond Health Care Centre at Vancouver Hospital. Women will be asked to undergo a heartbeat perception task and a sexual arousal assessment.

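### Hypothesis 8 (fewer breaks in the sexual response cycle) has no comparison with the control arm, and the plan does not say that hypothesis 3 takes precedence over the within-arm hypotheses 1 and 2

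*Combined protocol and SAP*

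**What the plan says.** All references are to the combined protocol and SAP.

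- **PURPOSE** asks an effectiveness question and names no comparator: to "determine whether an 8-session intervention is effective in reducing women’s sexual distress, improving their sexual response, and increasing their mindful skills".
- **HYPOTHESES, items 1 and 2** are change from baseline in one arm: "Compared to baseline, the MBCT group will have significant post-treatment improvements in self-report measures of" a list of scales, and "Compared to baseline, the MBCT group will have significant post-treatment improvements in laboratory physiological measures of" a list of laboratory outcomes.
- **HYPOTHESES, item 3** is the randomised contrast: "the changes in the endpoints listed in #1 or #2 will be significantly greater in the MBCT group than in the support group".
- **HYPOTHESES, item 8** names neither an arm nor a comparator: "participants with sexual desire issues will see an improvement (fewer breaks in the cycle) throughout the course of the eight-week treatment".
- **OBJECTIVES** is comparative. MBCT is to be tested in women "seeking treatment for low sexual interest/desire and/or arousal and compare it to a support group".
- **RESEARCH METHOD, Procedures**: "Participants will be randomly assigned to either the MBCT group or the support group (control condition". The support group is there to account for the education, discussion and support that both arms receive. It omits only the mindfulness practice.
- **Specification of Endpoints** makes sexual distress (FSDS-R) primary. Disruptions to the response cycle, recorded on a worksheet, are among the other endpoints.
- **Data analyses** gives a repeated measures ANOVA with group and time factors for a listed set of outcomes. Breaks in the response cycle are not on that list. A separate sentence says that their number and location will be examined, at first completion and at week 5, and mentions no group comparison.

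**The concern.** Women join because they currently have distressing concerns, and many are seeking care. Their scores may move without effective treatment, through natural course, familiarity with the measures, or regression to the mean. A before-after test cannot separate these from a treatment effect. The randomised support arm can, provided that the hypothesis uses it.

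Hypothesis 8 does not use it. If breaks fell equally in both arms, the hypothesis as worded would be confirmed, although the trial would have shown nothing about MBCT.

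For hypotheses 1 and 2 the gap is smaller. A controlled test of the same endpoints exists in hypothesis 3. What is missing is a statement of how to read a significant within-arm change alongside no difference between arms.

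**Working it through.** **1. Is there a controlled counterpart for each hypothesis?**

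| Hypothesis | Contrast as worded | Covered by hypothesis 3? | In the ANOVA list, with group factor? |
|---|---|---|---|
| 1 (self-report) | MBCT, post versus baseline | Yes | Yes |
| 2 (laboratory) | MBCT, post versus baseline | Yes | Mostly; C-reactive protein is not named |
| 8 (breaks in cycle) | Participants, over treatment | No, not in items 1 or 2 | No |

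Two other features might have supplied a control for hypothesis 8, but neither does.

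- The VENUS and community control data (Measures) are limited to demographics, the SIDI-F and the FSDS.
- The waitlist level of the time factor is not tied to any hypothesis. The extra pre-group visit is a sexual arousal assessment, and only women assessed more than 2.5 months before their group starts have it.

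**2. How often could a pre-post test succeed with no treatment effect?**

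The documents give no sample size, SD, correlation or expected drift, so there is no figure of the plan's own to reproduce. Everything below rests on assumed inputs.

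Inputs: two-sided alpha 0.05; n women in the MBCT arm; pre-post correlation r = 0.6; a shift d, in baseline SDs, from any cause other than treatment.

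- SD of change = sqrt(2(1 − r)) = sqrt(2 × 0.4) = 0.894.
- Noncentrality = (d / 0.894) × sqrt(n). For d = 0.3 and n = 50: 0.3355 × 7.071 = 2.372.
- The chance of a significant improvement is the upper tail of the noncentral t beyond the critical value (2.010 at 49 df), which is 0.64.

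| n | d = 0.2 | d = 0.3 | d = 0.5 |
|---|---|---|---|
| 30 | 0.22 | 0.43 | 0.84 |
| 50 | 0.34 | 0.64 | 0.97 |
| 70 | 0.45 | 0.79 | 0.996 |

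A shift common to both arms cancels in the difference between arms, so that test stays at 5%. If hypothesis 8 pools both arms, its n is larger and the chances are higher than those shown.

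**3. How much of this could be regression to the mean?**

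This depends on how selection works, which was examined by simulation (4,000 trials per setting, 20, 40 or 70 women per arm, no treatment effect). The selected fraction was set at the top 22.8%. That is the general-population figure for distress in JUSTIFICATION, borrowed only for illustration.

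- *Selection on the baseline score itself.* The selected mean is 1.325 SD above the population mean, and the expected fall is (1 − r) × 1.325: 0.53 SD at r = 0.6, 0.27 at 0.8 and 0.13 at 0.9. The within-arm test is significant in 25% (n = 20, r = 0.9) to 100% (n = 70, r = 0.6) of trials.
- *Separate earlier screen, serially correlated symptoms* (screen-baseline 0.85 to 0.90, baseline-post 0.70 to 0.80): 39% to 96%.
- *Separate earlier screen, independent transient error, no other drift*: 2.2% to 2.6%, the nominal rate in one direction.
- *Endpoint correlated only 0 to 0.3 with the selection variable, r = 0.7*: expected drift is at most 0.3 × 0.3 × 1.325 = 0.12 SD.

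In the first three settings the between-arm test was significant in 4.5% to 5.6% of trials. The fourth is a drift formula only.

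**The case against.** A reader might infer that the trial judges effectiveness on all of hypotheses 1, 2 and 8 by uncontrolled change, and that regression to the mean would confirm them. The documents do not support that reading, for four reasons.

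- **Hypotheses 1 and 2 have a randomised counterpart.** Hypothesis 3 covers their endpoints, JUSTIFICATION and OBJECTIVES frame the study as a comparison, and the ANOVA has a group factor. No stand-alone MBCT-only test is specified. Nor does any text say that a positive hypothesis 1 with a null hypothesis 3 would be reported as success; the plan is silent on that case.
- **Confirmation is possible, not certain.** There is no numeric entry cut-off, and pre-treatment measures are arranged after eligibility is confirmed. Under one plausible selection model the false-confirmation rate is only about 2.5%.
- **Regression to the mean is a weak mechanism for the laboratory measures.** Nobody is selected on genital response, heartbeat perception, hormone ratio or C-reactive protein. Habituation and repeat testing are likelier causes of drift there.
- **Hypothesis 3 does not test the whole programme.** Support shares everything but mindfulness practice, so resting every effectiveness conclusion on that contrast would invite misreading a null result.

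All four points stand, and they narrow the finding. None supplies a comparator for hypothesis 8 or states that hypothesis 3 takes precedence.

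**Conclusion.** The point holds in two parts. First, hypothesis 8 has no controlled test anywhere in the plan, so change unrelated to treatment could confirm it. Second, hypotheses 1 and 2 do have a controlled test, but the plan does not rank it above the within-arm claims. It would go too far to say that effectiveness on the endpoints of hypotheses 1 and 2 is judged without a control.

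The size cannot be fixed from the documents. On the assumed shift (0.2 to 0.5 SD), correlation (0.6) and arm size (30 to 70), false confirmation by a pre-post test runs from about 22% to over 99%. It falls to about 2.5% with a separate screen, independent transient error and no other drift. The between-arm test holds at about 5%.

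The effectiveness question in PURPOSE, if it means the whole 8-session programme, is not answered by either contrast. Within-arm change cannot show that the programme works, and a null difference from support cannot show that it does not.

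**What to change.** 1. Restate hypothesis 8 as an MBCT-versus-support difference in change in the number of breaks, and add the matching group comparison to Data analyses.
2. Confirm that both arms complete the Sexual Response Cycle Worksheet. The shared content implies it, but no section says so, and the worksheet is not in the numbered list under Measures.
3. Reconcile the timing: hypothesis 8 speaks of the full eight weeks, whereas the analysis is at first completion and week 5.
4. State that the group-by-time contrast (hypothesis 3), with the FSDS-R as primary, is the confirmatory test. Report the changes in hypotheses 1 and 2 as descriptive means with confidence intervals.
5. State that this contrast estimates the effect of mindfulness practice over the shared content, and limit conclusions about the whole programme accordingly.

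**Cost.** Rewording and analysis work only, provided both arms complete the worksheet. There will be fewer significant within-arm results to report, and hypothesis 8 will have lower power. With n women per arm, equal arms (the allocation ratio is not stated) and the same SD of change, the standard error of a between-arm difference is SD × sqrt(2/n). A pooled pre-post mean has SD / sqrt(2n). The ratio is sqrt(2/n) × sqrt(2n) = 2.

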After the conclusion of group session 8, women will be provided with an individualized link to online questionnaires, which will be nearly identical to those completed prior to their first assessment, and a second saliva sampling kit. In addition, women will repeat their sexual psychophysiological assessment at the UBC Sexual Health Lab. Women will also be asked about their experience with the mindfulness practices and/or sexuality worksheets at each post-treatment assessment. Questionnaires, at-home saliva sample collection, and the in-lab psychophysiological assessments will also be done 6 and 12 months after completing the 8-session group treatment. All online questionnaires for women in both treatment groups will be administered with SurveyMonkey™.

Participants who have completed the study will be invited to take part as a "patient partner," which will involve attending a focus group meeting with the study investigators to provide insight and feedback on their experience living with Sexual Interest/Arousal Disorder, as well as get their feedback on what they would find most interesting and relevant to viewers regarding the findings of another study called MODEST (Mood, Stress, and Sexual Desire in Women, CREB number = H10-02067), which also examined women's low sexual desire. This will help to develop a script to create a knowledge translation infographic video in the future. This meeting would take approximately 2 hours and patient partners would receive \$50 for their time and cost of parking. This is not a required study procedure but rather an invitation if former participants would like to share their experience. The meeting will be a single 2 hour session with up to three women with low desire, two facilitators, and a note-taker from the study team. The entire session will be audio-recorded and later transcribed. No individual names will be used in the transcript. Patient Partners will be asked to respect the confidentiality of those who attend this focus group meeting, and will be told that facilitators cannot control what other participants do with the information discussed, so that they can make an informed decision about whether or not to participate in the focus group.

Specification of Endpoints: The primary endpoint in this study will be sexual distress given that distress associated with impaired sexual functioning is the reason that women provide for

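### The main between-arm hypothesis spans 20 constructs, gives no success rule or visit, and is not linked to the primary endpoint

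*Combined protocol and SAP*

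**What the plan says.** The Objectives section sets the trial's aim as testing the mindfulness group and comparing it with a support group. Item 3 of the Hypotheses carries that comparison for the outcome measures. It predicts that "the changes in the endpoints listed in #1 or #2 will be significantly greater in the MBCT group than in the support group".

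The two lists it points to are:

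- **Item 1, self-report:** it opens with "a) sexual distress; (b) sexual desire, subjective sexual arousal, perception of genital arousal, and sexual pleasure". Parts (c) and (d) add one relationship score and two mood scores (rumination and depression). The stress and anxiety group is "e) perceived stress, general anxiety, anxiety sensitivity, and sexuality-related situational anxiety". Part (f) adds four more: non-attachment, self-compassion, mindfulness and a questionnaire measure of interoceptive awareness.
- **Item 2, laboratory:** parts (a) and (b) are genital response by photoplethysmograph and a heartbeat task for interoceptive awareness. The two saliva measures are "c) cortisol:DHEA ratio as measured by hormonal assays of saliva samples, and (d) a significant decrease in C-reactive protein".

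The endpoint hierarchy appears elsewhere, under Specification of Endpoints in the Research Method section: "The primary endpoint in this study will be sexual distress", measured with the FSDS-R. Desire, arousal, stress hormone ratios and interoceptive awareness are called secondary, and further measures are grouped as other endpoints.

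The Data analyses section applies one repeated measures ANOVA to all measures. Group is the between-subjects factor and time has five levels (waitlist, pre-group, post-group, 6 months, 12 months). It states no alpha, no primary contrast or visit, no testing order and no multiplicity adjustment.

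**The concern.** Naming a primary endpoint controls the error rate only if the trial's claim depends on that endpoint. Here the statement of what the trial expects to show between arms and the statement of what is primary are in different sections, and nothing joins them. Item 3 gives sexual distress no special role, and the analysis section does not supply one.

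A report that item 3 was supported on a secondary scale, with no difference on the FSDS-R, would therefore be compatible with the plan. The success rule could also be settled after the data are seen, because the text allows several.

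**Working it through.** The plan gives no alpha, error rate or sample size, so it has no figure of its own to reproduce. The check is a count followed by a range under stated assumptions.

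**1. Count of constructs (Hypotheses, items 1 and 2)**

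- Item 1: (a) 1 + (b) 4 + (c) 1 + (d) 2 + (e) 4 + (f) 4 = 16.
- Item 2: (a) to (d), one each = 4.
- Total: 16 + 4 = 20.

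**2. How many can be tested as documented**

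- General anxiety: the endpoint specification measures trait anxiety with the State-Trait Anxiety Inventory, but the Measures section lists the Trait Form as baseline only. If general anxiety means trait anxiety, no change can be computed.
- C-reactive protein is in item 2 but in neither the endpoint specification nor the analysis section.
- Without these two: 20 − 2 = 18. Some constructs, such as desire, have more than one instrument, so the number of tests could also exceed 20.

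**3. What item 3 could mean**

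The word *or* joins list 1 to list 2; within each list the items are joined by *and*. Assume two-sided alpha 0.05 per test, so 0.025 in the direction favouring MBCT, and no true effects.

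- *All endpoints of one list must succeed.* For either list the chance is at most 0.025, so for one or the other it is at most 0.025 + 0.025 = 0.05. There is no inflation.
- *Each endpoint is its own claim.* No single claim exists to be falsely confirmed. The expected number of false results is 20 × 0.05 = 1.0, of which 20 × 0.025 = 0.5 favour MBCT.
- *Any endpoint suffices.* If the tests are independent, the chance of at least one false result is 1 − (1 − a)^k.

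**4. The 'any endpoint' reading**

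- k = 20, favouring MBCT: 1 − 0.975^20 = 0.397.
- k = 20, either direction: 1 − 0.95^20 = 0.642.
- k = 18, favouring MBCT: 1 − 0.975^18 = 0.366.
- k = 18, either direction: 1 − 0.95^18 = 0.603.

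For correlated tests, 20 equicorrelated normal statistics were simulated (400,000 draws):

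| Common correlation | At least one favouring MBCT | At least one, either direction |
|---|---|---|
| 0 | 39.7% | 64.2% |
| 0.3 | 28.0% | 53.9% |
| 0.5 | 21.0% | 41.9% |
| 0.7 | 14.5% | 28.9% |
| 0.9 | 7.7% | 15.5% |

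Item 3 is directional, so the middle column is the relevant one. It assumes one directional contrast per construct.

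**5. With one pre-named FSDS-R contrast**

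The chance of a false confirmation is 5% two-sided, or 2.5% favouring MBCT.

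**The case against.** The strongest reply is that the hierarchy already exists. The endpoint specification names one primary endpoint, gives the reason and the instrument, and separates secondary from other endpoints. The Purpose section puts sexual distress first, and hypotheses 5 and 6 single out distress and desire. No section calls item 3 the main hypothesis; that label is used here because item 3 carries the stated objective across the outcome measures. A careful reader would see that a positive secondary scale with a null FSDS-R is a failed primary endpoint. This stands and limits the harm, but it leaves item 3 and the analysis section unlinked to that hierarchy.

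Four stronger readings are tempting, and the documents do not support them:

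- *Any one of the 20 satisfies item 3 as worded.* This is one possible reading. The plural phrasing and the *and* within each list fit the other two at least as well, and on the strictest there is no inflation.
- *Item 3 is the only between-arm hypothesis.* Hypothesis 7 also compares the arms, on participants' impressions of change.
- *Three post-treatment visits multiply the risk further.* The plan specifies a group-by-time ANOVA for each measure, not separate tests at each visit, and trait anxiety has no post-treatment measurement at all.
- *The risk is 64%.* That figure counts results in either direction and assumes independence. The Justification section itself reports high correlations between desire and arousal scores, so lower figures are more plausible for those scales.

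**Conclusion.** The point holds as a gap in linkage and wording. Item 3 covers 20 named constructs without a success rule, a visit or a tie to the FSDS-R, and the analysis section does not repair this.

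The size depends on the reading. If any endpoint suffices, the chance of a false result favouring MBCT runs from about 40% (independent tests) to about 8% (common correlation 0.9), against a nominal 2.5%. With 18 testable constructs the independent figure is 37% (60% in either direction). If all endpoints of a list must succeed, the risk is no more than 5%.

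Alpha, the common correlations and one contrast per construct are assumptions; the plan gives none of them. What the documents do establish is that the plan does not choose between these readings. They do not establish that the trial will claim success on any single endpoint.

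**What to change.** Reword item 3 so that it is confirmed only by the MBCT-versus-support difference in FSDS-R change, tested by one contrast named in advance. State the alpha and repeat the rule in the Data analyses section.

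The contrast can be a difference at one named visit or the single group-by-time test. A named visit gives a directional answer. The group-by-time test on five time levels has (2 − 1) × (5 − 1) = 4 degrees of freedom and no direction, so the plan should then say how direction will be judged.

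Label all other endpoints and visits, and hypothesis 7, as secondary with no confirmatory claim. Multiplicity-adjusted p-values beside the unadjusted ones are optional. If the investigators prefer to keep all 20 confirmatory, Bonferroni would require 0.05/20 = 0.0025 per test (familywise 1 − 0.9975^20 = 0.049 if independent), a much harder standard for the FSDS-R itself.

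Separately, align the lists: give general anxiety a post-treatment measure or remove it from item 3's scope, and do the same for C-reactive protein in the endpoint and analysis sections.

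Tying item 3 to the FSDS-R is a change of wording. It needs no added participants, visits or measures and uses the plan's own primary endpoint. The downside is that fewer secondary results can be presented as confirming the hypothesis.
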